## **1.0 Objectives / Specific Aims**

### **Aim 1: Evaluate the Safety, Feasibility, and Tolerability of High-Dose Repeated tDCS in Adults with Major Depressive Disorder**

#### **Aim 1:**

To evaluate the safety, tolerability, and feasibility of delivering high-dose transcranial direct current stimulation (tDCS) at 6 mA, administered twice daily for five consecutive days in an outpatient brain stimulation laboratory setting. Safety will be assessed by the absence of device-related serious adverse events (SAEs) (Protections (OHRP), 2010) requiring hospitalization or emergency care, and by skin assessments at each visit. Tolerability will be operationalized using the standardized tDCS Adverse Event Questionnaire (A. Brunoni et al., 2011). We hypothesize that  $\geq 80\%$  of participants will meet the “tolerated” classification, no device-related SAEs will occur, and the independent Safety Review Committee will not recommend stopping the study after reviewing safety/tolerability data from the first three participants in the run-in cohort.

### **Aim 2: Collect Preliminary Outcome Data on Depression Symptom Improvement and Mindfulness Following High-Dose Repeated tDCS**

This aim will explore whether high-dose, twice-daily transcranial direct current stimulation (tDCS) administered over five consecutive days leads to measurable improvements in depressive symptoms and state mindfulness. All participants (n = 20) will complete validated pre- and post-treatment clinical assessments, including the Patient Health Questionnaire-9 (PHQ-9) and the Snaith-Hamilton Pleasure Scale (SHAPS), to evaluate changes in mood and anhedonia. Additionally, participants will complete the Cognitive and Affective Mindfulness Revised (CAMS-R) before and after the intervention to assess changes in state mindfulness. Finally, we will also assess potential cognitive effects—both positive and negative—on working memory,

attention, and processing speed using the PROMIS Cognitive Function measure and the Trail Making Test. While this study is not powered to test efficacy, these exploratory data will help estimate effect sizes and inform the design of a future randomized controlled trial. We hypothesize that participants will show reductions in depressive symptoms, improvements in hedonic tone, and increases in state mindfulness following the stimulation protocol.

### **Aim 3: E-Field Modeling**

All participants will undergo a structural MRI to enable individualized retrospective E-field modeling. This modeling will estimate intracerebral current flow and assess the relationship between predicted dose and tolerability or symptom change. E-field modeling is exploratory and will serve to inform potential future dose-response modeling and precision targeting in follow-up studies.

### **2.0 Background**

Major Depressive Disorder (MDD) is a highly debilitating condition characterized by persistent sadness, impaired functioning, and significant morbidity, profoundly impacting individuals' quality of life and societal productivity (Stringaris, 2017). Despite advances in pharmacological and psychotherapeutic treatments, current estimates suggest that about 20-40% of patients continue to experience inadequate symptom relief (Touloumis, 2021).

Neuromodulation techniques, including transcranial direct current stimulation (tDCS), have emerged as effective alternatives or adjuncts for managing depressive symptoms. Numerous randomized controlled trials and meta-analyses have shown tDCS to be effective in alleviating acute depressive episodes, demonstrating moderate effect sizes across many studies (A. R. Brunoni et al., 2016; Couture et al., 2025; Moffa et al., 2020; Palm et al., 2016; Zheng et al., 2024). However, in spite of these findings listed above, tDCS has yet to achieve widespread clinical adoption or FDA approval, likely due to several high-profile randomized controlled trials that failed to differentiate either active treatment from sham stimulation (Blumberger et al., 2012; Loo et al., 2010, 2018) or noninferiority from the gold standard of antidepressant treatment (A. R. Brunoni et al., 2017). Contributing factors to these failed studies likely include: insufficient dose or short course length (Loo et al., 2010), treatment-resistant populations (Blumberger et al., 2012), active sham designs (Loo et al., 2018), and multisite variability with protocol heterogeneity (Loo et al., 2018). Furthermore, a review of the literature indicates that, in general, higher tDCS intensities — for example, 2 mA compared to 1 mA — are associated with greater clinical effects across a range of neuropsychiatric conditions (A. R. Brunoni et al., 2016; Evans et al., 2020; Moffa et al., 2020; Salehinejad et al., 2020; Zheng et al., 2024). In addition, recent studies employing accelerated protocols, higher cumulative total duration/dosing, and repeated daily sessions have demonstrated superior clinical outcomes (Couture et al., 2025; Moirand et al., 2022; Woodham et al., 2025), echoing innovations seen in TMS research with the high-dose SAINT protocol (Cole et al., 2022).

Nevertheless, the vast majority of clinical studies to date have limited stimulation intensity to  $\leq 2$  mA, despite substantial variability in the actual internal dose delivered to cortical tissue due to

individual differences in anatomy, scalp, and skull conductivity (Evans et al., 2020). This variability means that two individuals receiving the same applied current may experience markedly different effective brain doses, leaving the safety, tolerability, and potential efficacy of higher intensities largely untested. To address this gap, this study will look to establish the safety, tolerability, and feasibility of delivering repeated dosing at 6 mA stimulation using a modified Soterix Medical HC-1x1 tDCS system with high-capacity hydrogel electrodes in patients with MDD.

Recent dose-escalation studies in brain injury populations have confirmed safety and tolerability at 4 mA (Chhatbar et al., 2017; Nitsche & Bikson, 2017), while recent assessments tested with healthy volunteers indicate minimal discomfort and no significant skin injury even at 6 mA (Donnery et al., 2025). However, this device and dose have not been tested in a clinical or depressive patient population. Establishing feasibility and safety under these clinical conditions is critical to progressing toward a definitive efficacy randomized controlled trial (RCT) and expanding the therapeutic reach of tDCS for treating Major Depressive Disorder.

### **3.0 Intervention to be Studied**

The intervention we are studying is called high-dose transcranial direct current stimulation (tDCS). tDCS is a non-invasive form of neuromodulation that delivers a low-intensity electrical current through electrodes placed on the scalp to modulate cortical excitability. The device used in this trial is a modified version of the Soterix Medical 1x1 tDCS system, a platform with a strong safety record and use in hundreds of clinical trials worldwide. The modified “High Capacity” (HC-1x1) version in this study will be configured to deliver up to 6 mA of current with a ramp-up period extended from 60 seconds to 120 seconds to enhance comfort. In addition, the maximum voltage will be reduced approximately fivefold to improve tolerability further.

Stimulation will be delivered using self-adhesive hydrogel electrodes manufactured in the laboratory of [name], connected to the output of the modified 1x1 device. Electrodes will be positioned in a bifrontal montage, with the anode over the left frontal region and the cathode over the right frontal region. The device will be activated for 20 minutes per session, with twice-daily sessions separated by at least 30 minutes during the main protocol phase.

### **4.0 Study Endpoints**

#### ***Aim 1 Primary Endpoint: Safety, Feasibility, and Tolerability***

The proportion of participants meeting the “tolerated” classification as defined in Aim 1, based on data from the standardized tDCS Adverse Event Questionnaire and skin integrity assessments. “Tolerated” is defined as:

1. Completion of all scheduled tDCS sessions without discontinuation due to adverse events

2. No device-related serious adverse events (SAEs) requiring hospitalization or emergency care
3. No more than one transient Severe/Extreme symptom (score 4–5 on Likert scale) lasting  $\leq 30$  minutes without intervention
4. No clinically significant skin irritation, defined as skin redness  $\geq 3$  persisting  $>24$  hours or requiring medical treatment.

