**Day 1 (dose-escalation safety assessment cohort: first 3 patients enrolled):**

- 20-minute stimulation at **2 mA** → 30-minute rest period (extendable to 60 minutes if needed)
- 20-minute stimulation at **4 mA** → 30-minute rest period (extendable to 60 minutes if needed)
- 20-minute stimulation at **6 mA**

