**Day 2 (skin integrity and safety check):**

- Visual inspection of electrode sites for erythema, burns, or other skin reactions, and completion of the tDCS Adverse Event Questionnaire
- If no **serious adverse event (SAE)** requiring emergency department evaluation or hospitalization is observed, and skin integrity is deemed acceptable by clinical evaluation by on-site MD, participants will proceed to:
  - Two 20-minute stimulation sessions at **6 mA**, separated by a 30-minute-60 to 60-minute rest period for the remaining 4 days.
  - **Main Protocol (remaining 9 participants):** Progression beyond the initial safety run-in cohort will occur only after the Safety Review Committee has reviewed the adverse event data, skin integrity assessments, and tolerability questionnaire responses from the first three participants and determined that continuation at 6 mA is acceptable.
    - Same procedure as above, including consent, neuropsychological testing, pregnancy testing (if applicable), and MRI
    - Instead of starting at 2 mA, participants will start at 2 sessions/day at 6 mA (20 min each, 30-minute interval),
    - Conducted in-lab over 5 consecutive weekdays. After each session, skin and safety checks will be completed by study staff or trained personnel.

- **Post-Treatment Assessment:**

- Conducted in-person after the last stimulation session
- Virtual follow-up at 4 weeks to assess durability. Pt's will answer the same neuropsychological questions as above.

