#### **7. Cardiovascular Changes**

Transcranial direct current stimulation is not typically associated with heart-rate variability, but autonomic shifts cannot be ruled out. Vital signs will be obtained pre-session and once hourly during Days 1–7. Clinically significant hypotension/bradycardia ( $\geq 20$  % decline from baseline) will lead to dose reduction or discontinuation.

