#### **8. Device Malfunction**

Unintended rapid discharge or incomplete current delivery could result from device failure. Any malfunctioning of the device will be uploaded to RedCaps. Malfunctioning devices will be removed and quarantined for engineering review.

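### Criterion 1 of the primary 'tolerated' endpoint does not say how a participant whose dose was reduced for an adverse event is classified

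*Protocol*

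**What the plan says.** Aim 1 (protocol, Section 1.0) concerns stimulation "at 6 mA, administered twice daily for five consecutive days", and hypothesises that at least 80% of participants will be classed as tolerating it. Section 4.0 defines that class by four criteria. The first is "Completion of all scheduled tDCS sessions without discontinuation due to adverse events". The other three cover device-related serious adverse events needing hospital or emergency care, severe or extreme symptoms on the questionnaire, and clinically significant skin irritation. None mentions delivered current, session length or dose reduction.

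Section 10.0 gives every session a current and a length. The run-in ("dose-escalation safety assessment cohort: first 3 patients enrolled") has 20-minute sessions at 2, 4 and 6 mA on Day 1, then two 6 mA sessions a day. In the main phase, "participants will start at 2 sessions/day at 6 mA (20 min each, 30-minute interval". This section contains no reduction step.

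Section 15.0, item 7 (Cardiovascular Changes), says that clinically significant hypotension or bradycardia, set at a fall of 20% or more, "decline from baseline) will lead to dose reduction or discontinuation". It does not say whether 'dose' means current, session length or number of sessions.

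**The concern.** Section 15.0 treats dose reduction and discontinuation as alternatives after the same event, but criterion 1 names only discontinuation as a failure. A participant who stays in the trial at a lower current, or with shorter sessions, and attends every visit can therefore satisfy criterion 1 as worded. The primary proportion could then include someone who did not receive the regimen that Aim 1 asks about. Two assessors could classify the same record differently, and the looser reading can only raise the proportion.

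There is a minor consequence for Aim 3, which is to "assess the relationship between predicted dose and tolerability or symptom change". A reduced participant would be entered there as tolerating a dose that was not delivered, unless the modelling uses the delivered current.

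**Working it through.** The protocol gives no figure to reproduce on this point. The check is a reading of the text followed by an illustration of size.

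**1. How a reduced participant is classified.** Suppose the participant has a qualifying cardiovascular event, is reduced rather than discontinued, and attends every session.

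| What is reduced | 'Scheduled' means attendance only | 'Scheduled' includes current and duration |
|---|---|---|
| Current | meets criterion 1 | fails |
| Session length | meets criterion 1 | fails |
| Number of sessions | fails | fails |

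Criteria 2 to 4 do not settle the two divided rows. A fall in blood pressure or heart rate need not be a serious event needing hospital or emergency care, a severe or extreme questionnaire symptom, or a skin reaction.

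**2. Effect at the 80% boundary.** Section 6.0 gives 20 enrolled and 12 expected completers, so both are shown.

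- n = 12: 0.8 × 12 = 9.6, so at least 10 are needed. 10/12 = 83.3%; 9/12 = 75.0%. One participant is worth 1/12 = 8.3 points.
- n = 20: 0.8 × 20 = 16. 16/20 = 80.0%; 15/20 = 75.0%. One participant is worth 1/20 = 5.0 points.

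**3. How often the reading would decide whether 80% is met.** The protocol gives no reduction rate, so every rate here is an assumption. Let M ~ Bin(n, q) be the number reduced but otherwise passing, and S ~ Bin(n − M, p) the number of the others who tolerate. The two readings disagree when S < k and S + M ≥ k, with k = 10 or 16.

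| n | q | p = 0.70 | p = 0.80 | p = 0.90 |
|---|---|---|---|---|
| 12 | 0.1% | 0.002 | 0.004 | 0.003 |
| 12 | 1% | 0.024 | 0.035 | 0.027 |
| 12 | 2% | 0.047 | 0.070 | 0.055 |
| 12 | 5% | 0.113 | 0.172 | 0.149 |
| 20 | 0.1% | 0.003 | 0.004 | 0.002 |
| 20 | 1% | 0.029 | 0.044 | 0.018 |
| 20 | 2% | 0.058 | 0.088 | 0.038 |
| 20 | 5% | 0.137 | 0.217 | 0.118 |

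The result follows the assumed q almost entirely: about 0.2–0.4% at q = 0.1%, 2–9% at q = 1–2%, and 11–22% at q = 5%.

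**The case against.** The strongest reply is that 'scheduled' already carries the current and duration. Section 10.0 assigns both to every session and Aim 1 specifies 6 mA, so a session at another current is arguably not the scheduled one. This is a fair reading, and on it the reduced participant fails. It is not secured by the text, because criterion 1 names only discontinuation as the adverse-event failure.

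Second, the route is narrow. It rests on one clause in the risk section, about an effect which that section calls not typical. The reach of the clause is itself unclear: "Vital signs will be obtained pre-session and once hourly during Days 1–7" does not match a five-day course, and those passages must be reconciled. The problem also needs the reduction branch to be taken, current or length to be what is cut, full attendance, and a pass on criteria 2 to 4. All of this stands and limits the weight of the point. Rarity cannot be taken as established, however, since Section 2.0 says the device and dose are untested in a clinical or depressive population.

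Third, a statistical analysis plan, not available here, might classify modified exposure. That weakens the point but does not remove it, because the protocol itself fixes the definition and itself permits the path which the definition does not handle.

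Fourth, counting every reduction as failure is a choice; a separate category would also be defensible. This stands, and is the reason for reporting the count of reductions as well.

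A reader might also bring in device failure, since item 8 of Section 15.0 says that "incomplete current delivery could result from device failure". Criterion 1 is silent there too, but under-delivery through a fault is not intolerance, and item 8 already has malfunctions recorded. It adds little to this point.

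**Conclusion.** The point holds as an ambiguity in the primary endpoint definition, at low severity. Read literally, criterion 1 can count as tolerating 6 mA a participant whose current or session length was reduced for an adverse event; on another fair reading that participant fails.

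A reader might infer that the primary proportion will be inflated, or that Sections 4.0 and 15.0 contradict each other outright. The protocol supports neither. It gives no reduction rate, leaves 'dose' undefined in item 7, and admits a reading of 'scheduled' that closes the gap. Nor would a shift across 80% alter the conduct of the trial: 80% is a hypothesis, and continuation past the run-in depends on the Safety Review Committee's own review of adverse event, skin and questionnaire data (Section 10.0).

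The change in the proportion, 8.3 points per participant at n = 12 or 5.0 at n = 20, is plain arithmetic. How often it would change whether 80% is reached rests wholly on assumed rates.

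**What to change.** Reconcile Section 4.0 with Section 15.0, item 7, by wording criterion 1 as: *completion of all scheduled tDCS sessions at the current and duration scheduled for each session, without discontinuation or reduction due to adverse events*. Because the wording refers to each session's own schedule, the planned 2 mA and 4 mA run-in sessions count as scheduled. Report beside the primary proportion the number of participants with any reduction, so that the result can be read under either classification.

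The cost is one line, one reported count, and a record of current and duration for each session. The run-in has 3 + 4 × 2 = 11 sessions per participant and the main phase 5 × 2 = 10, which makes 3 × 11 + 9 × 10 = 123 sessions at n = 12, or 3 × 11 + 17 × 10 = 203 at n = 20. The tolerated proportion may be slightly lower, and a participant who does well after a small reduction will count as not tolerated. The change concerns classification only; it sets no dose and no clinical rule.

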### **1. Transient Skin Erythema / Redness**

Local redness or mild warmth is common beneath the stimulation pads. This reaction is expected to resolve within 30–60 minutes. Participants will be advised to apply vitamin E or an aloe-based cream if erythema persists longer than 2 hours. Any Grade  $\geq 2$  skin event will be documented and reviewed prior to the next stimulation day.

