### **2. Skin Irritation, Dermatitis, or Superficial Burns**

Prolonged or repeated sessions at higher current density may produce focal irritation, itching, or—rarely—superficial burn/necrosis. All electrode sites will be inspected before and after each session.

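### Criterion 4 of the primary tolerability endpoint leaves out burns and skin breaks, so an untreated superficial burn can be scored as tolerated

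*Protocol*

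**What the plan says.** The Aim 1 primary endpoint (Protocol, Section 4.0) is the proportion of participants who meet a four-part definition of tolerated. In summary:

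- Criterion 1: all sessions completed, with no stopping for an adverse event.
- Criterion 2: no device-related SAE that leads to hospital or emergency care.
- Criterion 3: at most one short-lived symptom scored 4–5.
- Criterion 4, the skin criterion: "No clinically significant skin irritation, defined as skin redness" of at least 3 that lasts more than 24 "hours or requiring medical treatment".

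Section 1.0 (Aim 1) hypothesises that at least 80% of participants will meet the definition. Section 6.0 plans 20 enrolled and 12 completed.

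Other sections treat skin harm more broadly. Section 15.0, item 2, says that stimulation "may produce focal irritation, itching, or—rarely—superficial burn/necrosis". The Day 2 check in Section 10.0 is a "Visual inspection of electrode sites for erythema, burns, or other skin reactions". Section 15.0, item 1, deals with ordinary redness: "Local redness or mild warmth is common beneath the stimulation pads", and "Participants will be advised to apply vitamin E or an aloe-based cream if erythema persists longer than 2 hours". The same item uses a skin grade of its own: a Grade 2 or higher "skin event will be documented and reviewed prior to the next stimulation day".

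**The concern.** Criterion 4 is the only part of the definition that looks at the skin. It looks at redness and at whether treatment was needed, not at the kind of lesion. The protocol foresees burns and inspects for them as something other than redness, but the primary endpoint has no place to count them. A participant with a burn could then add to the numerator of the figure meant to show that 6 mA through the new electrodes is tolerated.

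The treatment clause raises a smaller question. Medical treatment is not defined, and the protocol itself advises a topical cream for redness that outlasts 2 hours. If that cream were taken as medical treatment, redness well short of the 24-hour threshold might be scored as failure. If these matters are settled only once cases have been seen, the primary result depends in part on choices made after the data.

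**Working it through.** The protocol gives no calculation for this endpoint, so there is no stated figure to reproduce. The check is of the text, followed by a short calculation of size.

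**1. Can criteria 1 to 3 catch a burn?** Only through its consequences. Criterion 1 catches it if the participant stops treatment; a burn at the last session cannot cause that. Criterion 2 needs hospital or emergency care. Criterion 3 scores symptoms and allows one transient severe one. A superficial burn that leads to none of these passes all three.

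**2. Can criterion 4 catch it?** The clause can be parsed in two ways:

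- Reading A: (redness of 3 or more for over 24 hours) or (any irritation that requires medical treatment).
- Reading B: redness of 3 or more that either lasts over 24 hours or requires medical treatment.

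The table assumes that criteria 1 to 3 are met.

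| Skin event | Reading A | Reading B |
|---|---|---|
| Burn or blister, neither given nor judged to need treatment, redness below 3 or gone within 24 h | tolerated | tolerated |
| Burn with redness below 3, medically treated | fails | tolerated |
| Redness of 3 or more for over 24 h | fails | fails |
| Redness below 3 beyond 2 h, cream used and counted as medical treatment | fails | tolerated |
| Same, cream not counted | tolerated | tolerated |
| Redness of 3 or more, gone within 24 h, cream used and counted | fails | fails |
| Same, cream not counted | tolerated | tolerated |

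The first row does not depend on the reading: the untreated burn is tolerated either way. The cream rows do depend on choices that the text leaves open. For redness below 3 to fail, the cream must count as medical treatment and Reading A must apply.

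**3. The scale.** The endpoint uses a redness cut of 3 without naming a scale. Section 15.0, item 1, uses Grade 2 or higher for documentation and review. The protocol does not say whether these are the same scale.

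**4. Size.** One participant moves the proportion by 1/n:

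- n = 12: 1/12 = 8.3 points. The 80% hypothesis needs 10/12 = 83.3%, since 9/12 = 75.0%.
- n = 20: 1/20 = 5.0 points. It needs 16/20 = 80.0%, since 15/20 = 75.0%.

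The protocol gives no rate for skin events whose class depends on the wording. Taking a rate p as an assumption, the chance of at least one such participant is 1 − (1 − p)^n:

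| Assumed p | n = 12 | n = 20 |
|---|---|---|
| 2% | 0.215 | 0.332 |
| 5% | 0.460 | 0.642 |
| 10% | 0.718 | 0.878 |

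For burns alone the low end is the more relevant, since the protocol calls them rare.

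**The case against.** The strongest reply is that the gap is small. Section 15.0 describes burns as rare, and Sections 2.0 and 15.0 cite healthy-volunteer work at 6 mA without notable skin injury. Many burns would fail anyway, through lasting redness, stopping, emergency care, severe symptoms or (on Reading A) medical treatment. In the run-in, an on-site physician must find the skin acceptable on Day 2 before stimulation continues, and any Grade 2 or higher skin event is reviewed before the next stimulation day. Adverse events are documented at every session (Section 13.0), so a burn would be recorded whatever its endpoint class. All of this stands and narrows the case. It does not close it: Section 10.0 states no equivalent Day 2 gate for the main-protocol participants, and a record in the adverse event listing does not change how the primary endpoint is scored.

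It can also be said that self-applied aloe or vitamin E is self-care and would not ordinarily be called medical treatment. That is the more natural reading, and it is why the cream question is only an ambiguity. Nor does the protocol say that burns or blisters are managed with that cream; the advice concerns erythema.

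Finally, moving a proportion by 1/n is true of any binary endpoint. That is fair: those figures show scale and are not evidence of a defect specific to this criterion.

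**Conclusion.** The point holds in a limited form. As written, criterion 4 scores as tolerated a superficial burn or blister that is left untreated in a participant who completes all sessions, with redness below 3 or gone within 24 hours and without emergency care or excess severe symptoms. Where this happens, the primary proportion is too favourable for a harm that the protocol itself names. Each such participant is worth 8.3 points at n = 12 or 5 points at n = 20. How often it would happen cannot be derived from the protocol; the 2% to 10% range above is assumed. The undefined treatment clause and unnamed redness scale are secondary matters of clarity.

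Three stronger inferences are not supported:

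- A reader might infer that the Safety Review Committee would be misled by the proportion. Section 10.0 has it review the adverse event, skin and questionnaire data of the first three participants directly.
- A reader might infer that one burn, or one user of the cream, would reverse the trial's conclusion. The 80% is a hypothesis with no test or decision rule attached, and a single event crosses it only if the result lies right at the mark.
- A reader might infer that ordinary redness treated with the advised cream will be counted as failure. The text leaves this open but does not require it.

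**What to change.** Reword criterion 4 so that a participant fails for any one of:

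- (a) a burn, blister, skin break, ulceration or necrosis at an electrode site, whether or not treated;
- (b) redness of 3 or more persisting for over 24 hours;
- (c) a skin event that requires prescribed or clinician-delivered treatment.

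Also state that the cream advised in Section 15.0, item 1, does not by itself count as medical treatment for the endpoint. Name the scale behind the cut of 3, and reconcile it with the Grade 2 cut in that item. Record lesion type at the inspections already planned before and after each session.

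The cost is protocol wording and one field on the skin-check form. The tolerated proportion may come out slightly lower. The change affects endpoint classification only; stimulation, skin-care advice and rules for stopping stay as they are.
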